Comparison of Molecular and Cellular Properties of Converted DA Neurons from Fibroblasts of MDD/CSA (n=8), CSA/RES (n=4), and Psychiatrically Healthy Subjects (n=8): Once we optimize conversion of fibroblasts to mDA neurons, we will use these biopsied fibroblasts to convert them to mDA neurons using our optimized protocol. To evaluate whether converted DA neurons from each group have distinct properties, we will test their ability to synthesize and release DA in response to membrane depolarization. We will treat *in vitro* differentiated cells with 50 mM KCl for 30 minutes and assess DA release by HPLC. Media will be collected after 30 min then concentrated perchloric acid (PCA) will be added to a final concentration of 0.1 M PCA/0.1mM EDTA. The DA content of the supernatants will be measured by reverse-phase HPLC. We will also compare mRNA expression patterns for dopamine-related genes such as synthesizing (TH and AADC), uptake (DAT), degrading (MAO and COMT), and storage function (VMAT2) at mRNA and protein levels in converted mDA neurons of each group.

Plasma Samples

Concentrations of pro- and anti-inflammatory cytokines and related receptors will be assessed using enzyme-linked immunosorbent assays (ELISA, R&D systems, Minneapolis, MN). All assays will be performed at the CLIA-certified Harvard Catalyst Central Laboratory (HCCL) in accordance with manufacturer specifications, and will be run in duplicate.

b. Study endpoints

Not applicable

c. Statistical methods

Please see above.

d. Power analysis

Sample size and power calculations

Sample size was estimated after considering effect sizes obtained in preliminary studies. Effect sizes were calculated using $p = 0.05$ for detecting differences between (1) controls vs. CSA/MDD, and (2) CSA/MDD receiving a DA challenge vs. placebo. Based on these estimates and allowing for 5% data loss, the sample size is 92 (23 subjects/group). In our study using the PSST task proposed, relative to controls, women with histories of CSA and MDD showed lower accuracy in trials in which they needed to rely on reward (Cohen's $d = -0.85$). In a study using the probabilistic reward task, we found that unmedicated MDD subjects had significantly reduced response bias compared to controls ($d = -0.70$; [name] et al 2009b). In another study using the same task, we found that healthy subjects receiving

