a single dose of pramipexole – hypothesized to reduce phasic DA transmission due to inhibition of presynaptic autoreceptors – had significantly lower reward learning than those receiving placebo ($d = -1.45$; [name] et al 2008b). In an fMRI study using the MID task, relative to controls, a maltreated sample showed weaker activation to reward-predicting cues in the left putamen ($d = -0.54$) and left pallidus ($d = -1.02$), yielding a mean effect size of -0.78 . In a separate study using the MID task, unmedicated MDD subjects showed weaker activation than controls in response to gains in the caudate ($d = -0.98$), left NAc ($d = -0.73$) and left putamen ($d = -0.78$) during reward anticipation ([name] et al 2009a), yielding a mean effect size of -0.87 . In a pharmacological fMRI study in unmedicated MDD subjects we found that a single 150 mg dose of Bupropion – assumed to partially block DAT – increased reward-related responses in components of the brain’s reward circuit, including the midbrain ($d = -1.88$), subcallosal gyrus ($d = -1.64$), and SLEA ($d = -1.89$), leading to an mean effect size of -1.80 ([name] et al 2008a). In sum, based on the effect sizes we have observed for the behavioral (mean $d = -1.00$) and fMRI (mean $d = -1.15$) components, a total of 92 subjects leads to a power >0.95 of detecting group differences.

For the PET study, secondary analyses of altropane data collected in ADHD and control samples (Spencer et al 2007) indicated that a history of depression and/or current subthreshold depressive symptoms were linked to decreased DAT binding ($d = -0.58$). Because this sample was carefully screened to exclude current, clinically significant depressive symptoms and because analyses did not involve the recently developed Bayesian method, we expect that effect size between control and CSA/MDD groups will be larger (expected $d > 0.80$). Thus, 92 subjects leads to a power >0.85 of detecting group differences.

VII. RISKS AND DISCOMFORTS

a. Complications of surgical and non-surgical procedures

Maastricht Acute Stress Test (MAST)

The risks associated with the stress manipulation are minimal. This manipulation has been implemented in numerous labs due to its efficiency and safety. First of all, it is a non-intrusive manipulation that causes only very minor pain, if any. Secondly, at all times participants are allowed to remove their hand from the cold water and thus immediately stop the manipulation.

EEG

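### The stated power above 0.95 for group differences averages drug effects into the effect size; on the cited group effects alone, controls vs CSA/MDD has 0.73 to 0.76 two-sided, or 0.83 to 0.85 one-sided

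*Combined protocol and SAP*

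**What the plan says.** Section VI.d (Power analysis) uses p = 0.05 without saying whether tests are one- or two-sided. It names the differences to be detected as "1) controls vs. CSA/MDD, and (2) CSA/MDD receiving a DA challenge vs. placebo", and sets 92 subjects, 23 per group, allowing for 5% data loss. It then lists effect sizes, given here as absolute values:

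- Behaviour, group effects: PSST 0.85, where "women with histories of CSA and MDD showed lower accuracy in trials in which they needed to rely on reward"; PRT 0.70, where "unmedicated MDD subjects had significantly reduced response bias compared to controls".
- Behaviour, drug effect: 1.45. Healthy subjects given pramipexole "had significantly lower reward learning than those receiving placebo".
- fMRI (MID), group effects: a maltreated sample vs controls, 0.54 and 1.02, mean 0.78; MDD vs controls, 0.98, 0.73 and 0.78, "yielding a mean effect size of -0.87".
- fMRI, drug effect: mean 1.80. "In a pharmacological fMRI study in unmedicated MDD subjects we found that a single 150 mg dose of Bupropion" increased reward-related responses. No comparator or design is given.

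The section reduces these to 1.00 (behaviour) and 1.15 (fMRI) and states that "a total of 92 subjects leads to a power >0.95 of detecting group differences". For PET it expects d above 0.80 and states: "Thus, 92 subjects leads to a power >0.85 of detecting group differences".

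**The concern.** A drug effect says nothing about how far CSA/MDD women differ from controls. Both drug effects are much larger than the group effects beside them, so averaging the two kinds raises the d used to power the group contrast. The averaged d describes neither of the two targets.

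These sentences are the plan's only quantitative justification for 92 subjects. A reader would take a non-significant controls vs CSA/MDD result as carrying less than a 5% risk of a missed difference. Section V (Randomization) says the blind was broken in May 2016 for preliminary analyses. The correction therefore bears mainly on how null group results are read and reported.

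**Working it through.** **Method.** Two-sample t-test, noncentral t. Noncentrality = d × √(n1·n2/(n1+n2)), df = n1+n2−2, alpha 0.05. For 23 vs 23 the multiplier is √(529/46) = 3.391, df = 44, and the critical values are 2.015 (two-sided) and 1.680 (one-sided).

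**Step 1: reproduce the plan's means.** (0.85 + 0.70 + 1.45)/3 = 1.00. (0.78 + 0.87 + 1.80)/3 = 1.15. Both match, so the drug effects are inside both means.

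**Step 2: reproduce the plan's power at 23 vs 23.** d = 1.00 gives 0.912 two-sided and 0.955 one-sided. d = 1.15 gives 0.968 and 0.986. The stated figure is consistent with its own inputs if tests are one-sided.

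**Step 3: check the printed mean.** (0.98 + 0.73 + 0.78)/3 = 2.49/3 = 0.83, not 0.87.

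**Step 4: group effects only, controls vs CSA/MDD, 23 vs 23.** Behaviour: (0.85 + 0.70)/2 = 0.775. fMRI: (0.78 + 0.83)/2 = 0.805, or (0.78 + 0.87)/2 = 0.825 with the printed value.

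| Effect | d | Noncentrality | Two-sided | One-sided |
|---|---|---|---|---|
| Behaviour mean | 0.775 | 2.628 | 0.73 | 0.83 |
| fMRI mean | 0.805 | 2.730 | 0.76 | 0.85 |
| fMRI, printed 0.87 kept | 0.825 | 2.798 | 0.78 | 0.87 |
| PSST alone | 0.85 | 2.882 | 0.80 | 0.88 |

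Reaching 0.95 at 23 vs 23 needs d = 1.087 two-sided or 0.985 one-sided. No study-level group effect in the section is that large. One regional value, 1.02 for the left pallidus, would pass one-sided (0.96), but the plan itself averages it with 0.54.

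**Step 5: the n for tasks done after dosing.** Section V.a (fMRI Session) starts MID scanning one hour after amisulpride or placebo and gives the PSST after the scan. Half of each group receives placebo, so a placebo arm has 11 or 12 women. Hypothesis 1b concerns performance and activation under placebo. Two-sided:

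- CSA/MDD vs controls, 11 vs 12 (multiplier √(132/23) = 2.396): PSST at 0.85 gives 0.49; MID at 0.805 gives 0.45.
- CSA/MDD vs controls plus CSA/RES, 12 vs 23 (multiplier √(276/35) = 2.808): PSST 0.64; MID 0.59.

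**Step 6: the drug contrast.** Amisulpride vs placebo within CSA/MDD is also 11 vs 12. The averaged d gives 0.63 (d = 1.00) and 0.75 (d = 1.15) two-sided. At d = 1.45 it is 0.91. The section states no power for this target.

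**Step 7: PET, 23 vs 23.** d = 0.80 gives 0.756 two-sided and 0.848 one-sided; d = 0.81 gives 0.855 one-sided.

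**The case against.** **The calculation is sound on a one-sided reading.** This stands. One-sided tests at 23 vs 23 fit the behavioural, fMRI and PET statements together. The fault lies in the d, and it remains when tests are one-sided: 0.83 and 0.85.

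**Another contrast may have been meant.** At d = 0.775 and 0.805, CSA/MDD vs controls plus CSA/RES (23 vs 46) gives 0.85 and 0.87 two-sided, 0.91 and 0.93 one-sided. A four-group omnibus F with two high and two low means gives 0.88 and 0.90. Only both MDD groups vs both groups without MDD (46 vs 46) passes, at 0.96 and 0.97. Section VI.d does not name that split, and Section VI.a (fMRI Analyses) expects MDD and CSA/MDD to differ.

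**The group-only means also mix samples.** True: PRT comes from an MDD sample, and MID from a maltreated and an MDD sample. If CSA/MDD is the more impaired group, as the plan expects, these may understate the contrast. The matching value, PSST 0.85, still gives only 0.80 or 0.88.

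**Stronger readings that the documents do not support:**

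- *The PET figure is wrong.* The plan gives 0.80 as a lower bound, and one-sided power exceeds 0.85 just above it. Only the sidedness is undeclared.
- *Only placebo arms matter for MID.* Section VI.a also expects a Group main effect, which uses all 23 per group. The limit there is that the cited d values are from undrugged comparisons, while the plan expects amisulpride to bring CSA/MDD close to controls on placebo.
- *Hypothesis 1b is missed more than half the time.* That holds only for CSA/MDD vs controls (51% to 55%). Section VI.a sets CSA/RES with controls against CSA/MDD; pooling them gives 36% to 41%.
- *The drug contrast is secure because d = 1.80.* The bupropion comparator and design are not given, so that value cannot be carried to an 11 vs 12 between-subject comparison.

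**Conclusion.** The power stated for group differences does not hold for controls vs CSA/MDD, the group contrast the section names. On the plan's own group effects the risk of missing a true difference is 27% (behaviour) and 24% (fMRI) two-sided, or 17% and 15% one-sided, against an implied figure below 5%. The conclusion does not depend on sidedness or on the 0.87 slip, which is minor.

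This assumes the cited group effects apply to these samples, a t-test on 23 completers per group, and no further loss. Section IV.a plans for 23 per group completing at least two imaging sessions. If the 5% loss came out of the 23 (22 vs 22), the figures would be 0.71 or 0.81 for behaviour and 0.74 or 0.84 for fMRI. A planned ANOVA with pooled error would change them slightly: with error pooled over the four groups (88 df), two-sided power at 23 vs 23 is 0.74 and 0.77.

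**What to change.** In Section VI.d:

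1. Declare the sidedness and the contrast being powered. This also settles the PET sentence, which otherwise can stand.
2. Correct the mean of 0.87 to 0.83.
3. Remove the pramipexole and bupropion effects from the group-difference means.
4. Replace the figure above 0.95 with group-only power for controls vs CSA/MDD at 23 vs 23: 0.73 (behaviour) and 0.76 (fMRI) if two-sided, 0.83 and 0.85 if one-sided. Say which samples the d values come from.
5. Add the placebo-arm power for PSST and MID, two-sided: 0.49 and 0.45 for CSA/MDD vs controls; 0.64 and 0.59 for CSA/MDD vs controls plus CSA/RES.
6. State power for amisulpride vs placebo within CSA/MDD separately at 11 vs 12, as conditional on an assumed d (for example, 0.91 two-sided if d = 1.45, a pramipexole effect in healthy subjects). Do not rely on 1.80 unless its comparator and design are given.

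The cost is a text change and less favourable stated power. Design, sample size and planned tests stay as they are.

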
concentrations of electrolytes, BUN, SGOT, SGPT, CPK, alkaline phosphatase, total bilirubin, albumin, total protein, blood pregnancy test, TSH, eGFR, and electrocardiogram (EKG), and a urine drug test. These tests must be performed within four weeks prior to amisulpride administration.

Preliminary screening for sex, handedness, neurological disorders, exclusionary physical conditions, medication status, weight, history of childhood trauma and history of depression, and MRI and PET safety will take place at the time of the initial telephone contact or interview or via the online screening survey on RedCap (a Partners secure website). Subjects will be re-screened for MRI safety at the beginning of the fMRI session.

To avoid the confounding effects of medication, only subjects off medication will be considered. Importantly, no subject will be requested to discontinue treatment for the purpose of participating in the studies proposed here. Further, if any subject becomes emergently ill or suicidal, access to emergency clinical care will be provided according to established procedures at McLean Hospital. If at any point between signing of consent and the conclusion of the second session, a subject becomes suicidal, homicidal, manic, or psychotic, (s)he will be withdrawn from the study and appropriate care and resources will be provided. Depending on the outcome of the first session, eligible participants will be assigned to one of four groups: (1) CSA between the ages of 5-14 with current diagnosis of MDD (*CSA/MDD*), (2) CSA between the ages of 5-14 without current or past diagnosis of Axis I or II disorders (*CSA/RES*), (3) current diagnosis of MDD without a history of CSA (*MDD*), and (4) healthy controls. Each group will contain 23 subjects who complete at least two imaging sessions (n=23/group).

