Subjects will be paid \$15/hour for the SCID session (session 1), up to \$70 for the ERP session including \$38 for completing the EEG and up to \$32 on the probabilistic reward task, up to \$150 for the fMRI session including \$100 for completing the session and up to \$50 on the MID task, and \$200 for the PET session. In addition, participants who complete all four sessions of the study will earn an additional \$75. Lastly, if participants complete only part of a study session, they will be compensated in a prorated manner, such that if they complete half of a study session, they will be compensated half of the total amount (e.g., participant completes half of the PET scan session, he/she will be compensated \$100). If the participant completes all of the sessions, they can earn up to \$555. The subset of subjects who participate in the additional skin fibroblast study (n=20) will be compensated \$100.

Randomization

For protocol 2010-P-002593, all subjects in study are administered a single low dose of amisulpride (50 mg) in order to test the role of dopaminergic mechanisms in the pathophysiology of MDD. This proof-of-mechanism study uses a double-blind, placebo-controlled between-subject design (for each group in study, 50% of the subjects in each group will receive placebo, with the remaining 50% receiving a single dose of amisulpride), involves a single MRI session, and does not include a treatment component. Though data collection has not yet been completed, the blind was broken as of May 2016 to conduct preliminary analyses. Accordingly, the medication blind will be broken as of November, 2016 in order to allow further analyses. In order to preserve the scientific integrity of the study, we propose the following precaution:

The Research Assistant responsible for running participants ([name]), the study doctors ([name], [name]), and any other member of the [name] Lab who directly interacts with participants will remain blind to drug group assignment. Accordingly, if we discover during statistical analyses that a few participants yielded unusable data (e.g., due to excessive motion artifacts), we will be able to enroll and test a few final participants in a fully unbiased way.

b. Drugs to be used

Amisulpride

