A *Group* (CSA/MDD, CSA/RES, MDD, controls) x *Drug* (amisulpride, placebo) x *Trial Type* (PSST: Choose A, Avoid B or MID: Reward, loss, no-incentive) ANOVA will be run. Based on prior findings, we expect a significant *Drug x Trial Type* interaction, due to larger positive reinforcement learning but lower negative reinforcement learning in the amisulpride relative to the placebo group. Moreover, although amisulpride is expected to affect reinforcement learning in all groups, we hypothesize that CSA/MDD subjects will show the largest gains, leading to a significant *Group x Drug x Trial Type* interaction. Planned contrast will show no difference in positive reinforcement learning between controls receiving placebo and CSA/MDD subjects receiving amisulpride. To test Hypothesis 1b, a *Group x Drug x Trial* ANOVA is expected to yield no group differences between CSA/RES and controls and significant differences to the CSA/MDD in the placebo condition and CSA/MDD subjects receiving amisulpride.

fMRI Analyses

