Analyses will be conducted using FreeSurfer (Fischl et al 2002, 2004). Volumetric analysis will be conducted and, if applicable, fMRI data will be adjusted for volumetric group differences. Pre-processing will include motion/slice-time correction, removal of slow linear trends, intensity normalization, and spatial smoothing (6-mm). The hemodynamic response will be modeled as a gamma function (2.5 s delay to rise, 1.25 s dispersion time) and convolved with stimulus onsets. Data will be analyzed using two approaches: an ROI approach to evaluate *a priori* hypotheses and a whole-brain approach to test finding specificity. In the first, regression coefficients (“beta weights”) will be extracted from ROIs obtained from FreeSurfer’s parcellation and selected based on prior studies (Knutson & Cooper 2005). ROIs will include basal ganglia regions (globus pallidus, NAc, caudate, putamen), dorsal/ rostral anterior cingulate, vmPFC, and OFC. For each subject and ROI, beta weights will be entered into *Group* x *Condition* (amisulpride, placebo) x *Hemisphere* x *Trial* (reward, loss, no-incentive) ANOVAs. We expect that the main effects of *Group* (controls \approx CSA/RES > MDD > CSA/MDD) and *Condition* (amisulpride > placebo) will be significant. Moreover, although amisulpride will increase basal ganglia responses to reward – but not punishment or no-incentive – cues in all groups, we expect that the CSA/MDD group will show the greatest improvements (significant *Group* x *Condition* x *Cue* interaction). Planned contrast will show no difference between controls and CSA/RES receiving placebo, and CSA/MDD subjects receiving amisulpride will show similar activation as controls under placebo. In the second approach, whole-brain analyses will be run. Each subject’s data will first be re-sampled into Talairach space and random effects analyses will be run. Significance levels in the fMRI data will be set to yield a corrected mapwise significance level of $p < .05$.

PET Analyses

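### The stated power above 0.95 fits only a 23 v 23 group comparison; the drug comparison within CSA/MDD falls short of it at the same effect sizes, and the Group x Drug x Trial Type interaction has no stated power

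*Combined protocol and SAP*

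**What the plan says.** Section VI.d bases the sample size on effects "for detecting differences between (1) controls vs. CSA/MDD, and (2) CSA/MDD receiving a DA challenge vs. placebo", at p = 0.05 with sidedness not stated. It arrives at 92 women, 23 in each of four groups, after a 5% allowance for lost data. It then averages earlier effect sizes into d = 1.00 for behavior and d = 1.15 for fMRI and states that "a total of 92 subjects leads to a power >0.95 of detecting group differences".

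Amisulpride is a between-subject factor. Under Randomization in section V, "for each group in study, 50% of the subjects in each group will receive placebo", and the other half receive the drug. A group of 23 therefore splits into 11 and 12.

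Section VI.a tests the prediction that CSA/MDD women benefit most through an interaction. For the PSST and MID behavioral data, "we hypothesize that CSA/MDD subjects will show the largest gains, leading to a significant" Group x Drug x Trial Type interaction. For fMRI, "we expect that the CSA/MDD group will show the greatest improvements", to be shown by a Group x Condition x Cue interaction. No effect size, variance or power is given for any interaction. Study endpoints (VI.b) are marked not applicable, and no test is named as primary.

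**The concern.** One power figure closes the behavioral and fMRI part of the power section, but the analyses that follow rest on samples of very different size. The group comparison uses 23 v 23. The drug comparison inside CSA/MDD uses 11 v 12. The largest-gain prediction compares drug effects across groups, each estimated from 11 v 12.

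What is at stake is how a null result would be read. If the interaction has modest power, a non-significant result is quite likely even when CSA/MDD women do respond most. Without a power statement or a confidence interval, that result could be taken as evidence against the hypothesis.

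**Working it through.** **Inputs.** From VI.d: 23 per group; pooled d = 1.00 and 1.15; cited drug effects d = 1.45 (pramipexole, behavioral) and 1.80 (bupropion, fMRI). From section V: 1:1 drug allocation within group. Alpha is 0.05, two-sided unless stated. All 23 per group are taken as analysed, which is favourable: the 23 are defined in IV.a as completing at least two imaging sessions, so fewer may have fMRI data.

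**1. What was pooled.** (0.85 + 0.70 + 1.45)/3 = 1.00 and (0.78 + 0.87 + 1.80)/3 = 1.15. Each mean mixes two group differences with one drug effect. None of the inputs is an interaction effect.

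**2. The plan's figure.** Two-sample t, noncentrality d/√(1/n₁ + 1/n₂). For 23 v 23, √(2/23) = 0.295 and df = 44.
- d = 1.00: noncentrality 3.39, power 0.955 one-sided, 0.912 two-sided.
- d = 1.15: noncentrality 3.90, power 0.986 one-sided, 0.968 two-sided.

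So the figure above 0.95 reproduces for this comparison, but at d = 1.00 only one-sided.

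**3. Second sizing comparison, drug v placebo in CSA/MDD.** √(1/11 + 1/12) = 0.417, df = 21. Two-sided power is 0.63 (d = 1.00), 0.75 (1.15), 0.91 (1.45) and 0.98 (1.80).

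**4. Interaction.** Give each woman a trial-type score, reward minus comparison trials. A drug effect in one group has variance v = 1/11 + 1/12 = 0.174 in units of the score SD. A difference between two groups' drug effects has variance 2v = 0.348, against 2/23 = 0.087 for 23 v 23, four times as large.

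The 3-df test has λ = Σ(δ_g − mean δ)²/v and 84 error df. If only CSA/MDD responds by d, λ = 0.75d²/v, which is 4.30 at d = 1.00 and 5.69 at 1.15. If d applies to reward trials only and the correlation between trial types is r, the effect on the score is d/√(2(1 − r)), which equals d at r = 0.5. The documents give no r.

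| Scenario | Power, lower d | Power, higher d |
|---|---|---|
| CSA/MDD only, r = 0.5, d = 1.00 / 1.15 | 0.37 | 0.48 |
| Same, r = 0 | 0.20 | 0.25 |
| Same, r = 0.8 | 0.77 | 0.89 |
| r = 0.5, other groups show half the effect (λ = 0.1875d²/v) | 0.12 | 0.14 |
| r = 0.5, CSA/MDD only, d = 1.45 / 1.80 | 0.69 | 0.88 |
| r = 0.5, CSA/MDD only, d = 1.00 / 1.15, loss-type trials move equally the other way (score effect 2d) | 0.94 | 0.98 |

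**5. A matching 1-df contrast.** CSA/MDD drug effect minus the mean drug effect of the other three groups: variance v(1 + 1/3) = 0.232, SE 0.482. If only CSA/MDD responds (r = 0.5), noncentrality is 2.07 and 2.39, power 0.54 and 0.66. With half effects elsewhere it is 1.04 and 1.19, power 0.18 and 0.22.

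**6. If 184 were analysed.** Section III.b gives 184 women. At 23 per cell, first-row assumptions, 3-df power is 0.68 and 0.81.

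**The case against.** The strongest reply is that the plan claims its figure only for group differences and names the comparisons behind it, neither of which is an interaction. That stands. A reader might infer that the stated power is a miscalculation; it is not, since it reproduces for 23 v 23. What is missing is a power statement for the other tests.

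A reader might also infer that the interaction is the principal test of Aim 1. The documents do not say so. No test is primary, VI.a also expects a Drug x Trial Type effect pooled over groups, and a pooled drug effect at 46 v 46 has power above 0.99 at d = 1.00. Planned contrasts are listed too.

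Nor is 0.37 to 0.48 the power at the plan's own interaction effect, because the plan gives none. The assumed correlation drives the result. For the PSST, VI.a predicts better positive but poorer negative reinforcement learning under the drug; if those shifts were equal and confined to CSA/MDD, power would be 0.94 to 0.98. Against this, VI.a expects the fMRI response to be specific to reward cues, and it expects the drug to act in all groups, which pulls power down.

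It is also tempting to suppose that the three MID trial types lower power further. With reward-only response, r = 0.5 and sphericity, the 6-df test gives 0.37 and 0.49, essentially unchanged.

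Finally, if the cited drug effects of 1.45 and 1.80 were meant for the 11 v 12 comparison, one-sided power is 0.957 and 0.994. That defence needs VI.d to state both the effect size and the sidedness, which it does not.

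**Conclusion.** The point holds as a gap in the power section. The stated figure is sound for 23 v 23 at the pooled effect sizes, one-sided at d = 1.00. At those same sizes it does not extend to the plan's own 11 v 12 drug comparison, where two-sided power is 0.63 to 0.75.

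For the interaction, only a conditional statement is possible. If it is 1.00 to 1.15 SD of the trial-type score and confined to CSA/MDD, 3-df power is about 0.37 to 0.48. The scenarios tabulated above run from 0.12 to 0.98. The fourfold variance follows from the layout alone; the power values rest on an assumed effect pattern and correlation. The documents do not support a claim that the interaction is underpowered under every reasonable assumption, but they give no basis for treating it as covered by the stated figure.

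**What to change.** **In VI.d:**
- Limit the statement above 0.95 to the 23 v 23 comparison and state its sidedness.
- Add power for drug v placebo within CSA/MDD at 11 v 12, naming the effect size used.
- Give interaction power as a range with its assumptions: which groups respond, which trial types respond, and the correlation between them.
- Reconcile 92 here with 184 in III.b, and say how many are expected per Group x Drug cell with usable fMRI data.

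**In VI.a:**
- Name a 1-df contrast for the largest-gain prediction: the CSA/MDD drug effect on the reward-specific score minus the mean drug effect of the other three groups.
- Report its confidence interval, and state that a non-significant result is inconclusive.
- Record that the contrast was added after the blind was broken in May 2016 for preliminary analyses, so that readers can weigh it accordingly.

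The cost is wording in VI.d and one dated contrast in VI.a, with no extra subjects. The stated power becomes less favourable, and a contrast added after unblinding carries less confirmatory weight than one fixed beforehand.
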